6.2.2. Secondary Endpoints

The secondary endpoints of the study are as follows:

- the annualized number of bleeding episodes (spontaneous and traumatic) per subject
- the annualized number of spontaneous joint bleeding episodes per subject
- assessments of response to treatment with rFIXFc for bleeding episodes, using the 4-point bleeding response scale (Investigator assessment for bleeding episodes treated in the clinic; parent or caregiver assessment for all other bleeding episodes)
- the total number of EDs per subject per year
- total annualized rFIXFc consumption per subject for the prevention and treatment of bleeding episodes

CONFIDENTIAL

The information contained herein may not be used, disclosed, or published without the written consent of Bioverativ Therapeutics Inc

- the number of injections and dose per injection of rFIXFc required to resolve a bleeding episode
- rFIXFc incremental recovery

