- the reason for administering the dose (medical or nonmedical reasons [e.g., training for administration of study treatment])
- the caregiver's rating of treatment response

CONFIDENTIAL

The information contained herein may not be used, disclosed, or published without the written consent of Bioverativ Therapeutics Inc

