10.5. Non-Medical Treatment With rFIXFc

During the study, subjects' parents/caregivers or subjects may attend training sessions on administration of rFIXFc. Administration of rFIXFc for training purposes will be considered nonmedical treatment. Such training is permitted and must be recorded in the EPD. However, subject/parent/caregiver administration with the first dose of rFIXFc must be performed under supervision in the clinic. Data from this time period will be excluded from the analysis of consumption.

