16. STATISTICAL METHODS AND DETERMINATION OF SAMPLE SIZE

In general, all statistical analyses will be descriptive in nature. No formal comparison is planned and no hypothesis will be formally tested. Continuous variables will be summarized and presented by the number of observations, mean, median, standard deviation, minimum, and maximum. Categorical variables will be summarized by the number and percentage in each category.

The objectives of the study and the endpoints to be analyzed are listed in Section 6.

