##### **5.4.2.1. Adjustments Due to Surgical/Rehabilitation Periods**

For analysis purposes, the efficacy period for a given treatment regimen will be adjusted for all surgical/rehabilitation periods (major and minor). The start and end of the efficacy period for a given treatment regimen are adjusted as follows:

	Statistical Analysis Plan	Final v1.0
---	----------------------------------	-------------------

- For patients on a prophylactic regimen before the start of a surgical/rehabilitation period, the efficacy period for the prophylactic regimen continues up to the last dose (for prophylaxis or bleeding) before the start of the surgical/rehabilitation period.
- For patients on the episodic regimen before the start of a surgical/rehabilitation period, the efficacy period for the episodic regimen continues up to 1 minute before the start of a surgical/rehabilitation period.
- For patients on a prophylactic regimen following the end of a surgical/rehabilitation period, the efficacy period for the prophylactic regimen starts or re-starts at the first prophylactic dose following the end of the surgical/rehabilitation period.
- For patients on the episodic regimen following the end of a surgical/rehabilitation period, the efficacy period for the episodic regimen starts or re-starts at 00:01 on the day following the end of the surgical/ rehabilitation period.

Start and end dates/times for the efficacy period for given treatment regimens and treatment regimen changes will be adjusted for each surgery (major or minor) as necessary.

For patients on a prophylactic regimen before the start of a surgical/rehabilitation period, the interval of time between the last dose before the surgical/rehabilitation period and the start of the surgical/rehabilitation period will not be attributed to the efficacy period for the prophylactic regimen. By definition, there should not be any treated bleeding episodes in this interval of time.

For patients on a prophylactic regimen following the end of a surgical/rehabilitation period, bleeding episodes that occur after discharge from a rehabilitation facility but before the next prophylactic dose will be attributed to the surgical/rehabilitation period and hence not counted towards the annualized bleeding rate (ABR).

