#### **6.6. Study Drug**

Study treatment is described in Section 3.1.2. Study drug administered will be listed by patient for the FAS. This will include the reason for administration (PK assessment, episodic (treatment of a bleeding episode), prophylaxis, ITI, surgery, other), date and time of administration, dose and dosing intervals, consumption and compliance. It will also include lot number and nominal potency of the lots used.

Except for PK doses, the unit body weight dose (IU/kg) for analysis of dosing will be calculated as the total IU (nominal dose) for each injection divided by the patient’s most recent weight in kg prior to the dose of study drug.

PK doses are all 50 IU/kg at the Baseline IR Visit and the ITI regimen IR assessments, and are calculated using the actual potency of the vial (between 80 to 125% of nominal strength) and using partial vials where necessary. Therefore PK doses in the analysis are similarly calculated using the exact number of complete and partial vials, the volume and actual potency of each vial and the patient’s most recent weight.

Both types of dose are calculated as follows:

$$\text{Dose (IU/kg)} = \frac{\left( \frac{\text{Total volume administered}}{\text{Volume of vial}} \right) \times \text{Actual/Nominal Potency of Vial}}{\text{Weight (kg)}}$$

PK doses are not used for the purpose of preventing or treating bleeding and therefore the total annualized rFIXFc consumption will exclude the IU/kg amount that is used for PK doses. However, data collected over the time in which the PK dose was administered will be included in the safety analyses.

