#### 6.6.1.4. Consumption

The total annualized rFIXFc consumption (IU/kg) will be calculated for each patient using the following formula:

$$\text{Annualized consumption} = \frac{\text{Total IU/kg of rFIXFc during the efficacy period}}{\text{Total number of days during the efficacy period}} \times 365.25$$

The total amount of rFIXFc received will be the sum of the nominal IU/kg administered for each injection based on the units of rFIXFc as recorded from the patient's EPD and eCRF and his most recent weight.

Total annualized rFIXFc consumption per patient will be determined for the efficacy period (i.e., excluding the PK assessments and surgery/rehabilitation periods [major surgeries]). Total annualized consumption per patient will also be derived based on treatment regimen and overall.

Consumption is a secondary endpoint in this study. A description of how consumption will be summarized is described in Section 7.4.7.

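### The SAP does not carry over the protocol's exclusion of training injections from the consumption analysis, so annualized rFIXFc consumption could be overstated

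*SAP*

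**What the plan says.** **Endpoint.** Protocol 6.2.2 names as a secondary endpoint "total annualized rFIXFc consumption per subject for the prevention and treatment of bleeding episodes".

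**Protocol rule.** Section 10.5 states: "Administration of rFIXFc for training purposes will be considered nonmedical treatment". It requires training doses to be recorded in the electronic diary and adds: "Data from this time period will be excluded from the analysis of consumption". Section 10.2.3.2 lists among the diary items "the reason for administering the dose (medical or nonmedical reasons [e.g., training for administration of study treatment".

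**SAP rule.** Section 6.6.1.4 divides total IU/kg in the efficacy period by days in the efficacy period and multiplies by 365.25. The IU/kg total runs over each injection in the diary and eCRF. On exclusions it says: "Total annualized rFIXFc consumption per patient will be determined for the efficacy period (i.e., excluding the PK assessments and surgery/rehabilitation periods [major surgeries". Section 6.6 adds that "total annualized rFIXFc consumption will exclude the IU/kg amount that is used for PK doses", because those doses serve neither to prevent nor to treat bleeding. Section 7.4.7 refers back to 6.6.1.4 and adds no exclusion.

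**Efficacy period.** SAP 5.4.2.1 states that "the efficacy period for a given treatment regimen will be adjusted for all surgical/rehabilitation periods (major and minor". SAP 5.4.2.2 also removes prophylaxis gaps longer than 28 days. Neither section mentions training.

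**Declared changes.** SAP 10 lists three differences from the protocol: the Full Analysis Set, the dropped Supporting Analysis Set and the health outcomes questionnaire. The consumption rule is not among them.

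**The concern.** The protocol has an explicit exclusion that the SAP does not implement. The SAP's own reason for dropping PK doses applies equally to training doses, yet only PK doses are dropped by purpose. Programmed as written, the SAP counts a training injection that falls in the efficacy period, and the reported figure no longer measures only what the endpoint names.

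At stake is the accuracy of a secondary endpoint reported by regimen. The primary inhibitor endpoint, the exposure-day counts and the safety analyses do not depend on this rule.

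**Working it through.** The documents give no consumption figure, so there is nothing to reproduce. The check applies the SAP 6.6.1.4 formula with and without training doses.

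**Inputs**
- Formula: consumption = total IU/kg ÷ days × 365.25 (SAP 6.6.1.4).
- Regimen: 50 IU/kg every 7 days, the recommended starting prophylaxis (Protocol 10.2.2.2), used only as an illustration.
- Follow-up: 182, 350 and 1,092 days, spanning the expected 6 months to 3 years (Protocol 7.3). At weekly dosing these hold 26, 50 and 156 doses.
- Training doses: number and size are not given. Assumed 1 to 5 doses of 50 IU/kg inside the efficacy period.

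**Case A: the training dose is extra to the schedule**

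| Days | Training dose excluded | One training dose counted | Difference |
|---|---|---|---|
| 182 | 1,300/182 × 365.25 = 2,608.9 | 1,350/182 × 365.25 = 2,709.3 | 1/26 = +3.8% |
| 350 | 2,500/350 × 365.25 = 2,608.9 | 2,550/350 × 365.25 = 2,661.1 | 1/50 = +2.0% |
| 1,092 | 7,800/1,092 × 365.25 = 2,608.9 | 7,850/1,092 × 365.25 = 2,625.7 | 1/156 = +0.6% |

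The effect is proportional to the number of doses. Five give 5/26 = +19.2%, 5/50 = +10.0% and 5/156 = +3.2%. If the excluded dose also takes one day out of the denominator, the single-dose differences become +3.3%, +1.7% and +0.55%.

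**Case B: the training dose replaces a scheduled dose (350 days)**
- SAP as written: 2,500/350 × 365.25 = 2,608.9.
- Dose removed, days kept: 2,450/350 × 365.25 = 2,556.8. The SAP value is 2.0% above this.
- Dose and its 7-day interval removed: 2,450/343 × 365.25 = 2,608.9. There is no difference.

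In Case B, removing the dose alone would lower the figure by 2.0% although the patient's weekly consumption had not changed.

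**Case C: a short episodic period, for sensitivity only**
- Two bleed doses in 182 days: 100/182 × 365.25 = 200.7. One added training dose gives 150/182 × 365.25 = 301.0 (+50%).
- Four bleed doses in 182 days: 200/182 × 365.25 = 401.4. One added training dose gives 250/182 × 365.25 = 501.7 (+25%).

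No passage supports these bleed counts. The cases show only that the relative effect grows as the number of other doses falls.

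**Surgery bracket.** The 6.6.1.4 formula takes both IU/kg and days from the efficacy period. SAP 5.4.2.1 has already cleared that period of major and minor surgical periods. Doses and days of a minor surgery therefore leave together, and the bracket disagrees only as a description.

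**The case against.** **The efficacy period belongs to the SAP.** Protocol 16.2.2 lets the SAP define that period and bases consumption on it. This delegates the definition of periods. It does not cancel the specific exclusion in Protocol 10.5, and SAP 5.4.2 removes no training time.

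**SAP 10 claims to list only major differences.** That is fair, and the omission may be an oversight. The rule as written still departs from the protocol without saying so.

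**The effect may be small.** This stands. Consumption is descriptive: "No formal comparison is planned and no hypothesis will be formally tested". Nothing says how many training doses were given or whether they were extra to schedule.

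**Training doses may be hard to identify.** This stands in part. Protocol 10.1.2 sends injections given at a site visit to the eCRF and bars them from the diary. Protocol 10.5 wants training in the diary, yet requires the first caregiver-given dose to be supervised in clinic. The reason lists in SAP 6.6 and 6.6.1.1 have no training category, so placing these doses under 'other' is an inference. A filter on the diary alone could miss clinic training.

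A reader might infer three stronger points that the documents do not support:
- *Minor-surgery doses stay in the numerator after their days have left.* The formula rules this out, as shown above.
- *The distortion is concentrated in the episodic group, at around +50%.* That size needs assumed bleed counts. No passage says training clusters there; Protocol 7.3.2 and 10.2.2.2 describe home-administration instruction alongside prophylaxis.
- *Protocol 10.5 requires removing the dose alone.* It speaks of data from a time period and does not say whether days go too.

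**Conclusion.** The point holds as a gap between protocol and SAP. As written, the SAP counts training injections that Protocol 10.5 excludes, and no other SAP rule removes them.

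Consumption could be overstated; that it will be is not established. In the cases computed, the SAP value is equal to or above the value with training excluded. Per dose, the excess on weekly prophylaxis is about 3.8% at 182 days, 2.0% at 350 days and 0.6% at 1,092 days. It is nil when a training dose replaces a scheduled one and its interval is removed as well. These figures assume 50 IU/kg training doses that fall inside the efficacy period. In a short episodic period with few doses the relative effect can be larger, but the documents do not allow it to be sized.

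This should be corrected before the analysis is programmed. It does not threaten the study's main conclusion.

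**What to change.** 1. In SAP 6.6 and 6.6.1.4, state that injections recorded as nonmedical or training are excluded from annualized consumption, as Protocol 10.5 requires.
2. State how time is handled. If the training dose is extra to schedule, remove the dose only. If it replaces a scheduled dose, remove the dose and its interval.
3. Identify these doses from both diary and eCRF records, and say how a clinic training dose without a nonmedical flag will be recognised.
4. Keep training doses in injection counts, exposure days and safety.
5. As a wording alignment only, change the major-surgery bracket in 6.6.1.4 to match the major and minor surgical periods in 5.4.2.1.

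If the sponsor prefers to count training doses, SAP 10 should declare and justify the departure.

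The cost is a few sentences and a programming filter. The diary field already exists; the extra work is checking eCRF records for training given in clinic.

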16.2. Efficacy

16.2.1. Analysis Population

Subjects who receive at least 1 dose of rFIXFc study drug will be included in the FAS. Efficacy analyses will be based on the FAS including the data collected on or after the time of the first injection of rFIXFc study drug.

Subjects developing a confirmed positive inhibitor test after exposure to rFIXFc study drug (the Inhibitor Subgroup) will have their efficacy data included up to the time of the last negative inhibitor test; efficacy data collected after the time of the last negative inhibitor test will be summarized separately.

CONFIDENTIAL

The information contained herein may not be used, disclosed, or published without the written consent of Bioverativ Therapeutics Inc

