#### **2.2.2. Secondary Endpoints**

The secondary endpoints of the study are as follows:

- The annualized number of bleeding episodes per patient (annualized bleeding rate [ABR]).
- The annualized number of spontaneous joint bleeding episodes per patient.
- Assessments of response to treatment with rFIXFc for bleeding episodes, using the 4-point bleeding response scale (Investigator assessment for bleeding episodes treated in the clinic; parent or caregiver assessment for all other bleeding episodes).
- Total number of EDs per patient per year.
- Total annualized rFIXFc consumption per patient for the prevention and treatment of bleeding episodes.
- The number of injections and dose per injection of rFIXFc required to resolve a bleeding episode.
- rFIXFc incremental recovery (IR).

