### 5.3.2. End Date and Time of the Last Treatment Regimen

The end of the last treatment regimen will be either:

- The date and time of the last rFIXFc dose for patients whose last treatment regimen was prophylaxis, ITI, or if they ended the study in a surgical/rehabilitation period.
- At 23:59 on the day of the last non-safety follow-up study visit for patients whose last treatment regimen was episodic.

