#### **5.4.2. Efficacy Period**

The efficacy period will be used for the evaluation of efficacy and health outcome endpoints. For a patient to have an evaluable efficacy period over the duration of study, he must have at least 1 day of treatment for an episodic regimen or at least 2 prophylactic injections for prophylactic regimens.

The start and end, and the total duration of the efficacy period for a given treatment regimen is the same as the start and end, and the total duration of that treatment regimen defined in Section 5.3.4 with the exceptions described in the following two subsections. The start of the efficacy period for each patient is the start of their first treatment regimen and the end is the end of their last.

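### The per-patient overall annualized consumption in SAP 6.6.1.4 includes ITI doses and days, contrary to the endpoint definition and to the protocol's separation of post-inhibitor data

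*SAP*

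**What the plan says.** The secondary endpoint in SAP 2.2.2 is "Total annualized rFIXFc consumption per patient for the prevention and treatment of bleeding episodes". SAP 6.6.1.4 computes it as total IU/kg in the efficacy period, divided by days in that period, times 365.25, and adds: "Total annualized consumption per patient will also be derived based on treatment regimen and overall".

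SAP 5.4.2 defines when a patient's efficacy period opens and closes: "the start of their first treatment regimen and the end is the end of their last". ITI is one of three regimens in SAP 3.1.2, and SAP 5.3.2 gives the end of the last regimen as "The date and time of the last rFIXFc dose for patients whose last treatment regimen was prophylaxis, ITI", or in a surgical period.

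The removals are surgical/rehabilitation periods (5.4.2.1), gaps over 28 days within prophylaxis (5.4.2.2) and PK doses. SAP 6.6 gives the reason for the last: "PK doses are not used for the purpose of preventing or treating bleeding and therefore the total annualized rFIXFc consumption will exclude" them.

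Protocol 16.2.1 says that, for patients with a confirmed inhibitor, "efficacy data collected after the time of the last negative inhibitor test will be summarized separately". Protocol 16.2.3 plans an overall summary of consumption.

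**The concern.** ITI doses are given to induce tolerance. SAP 6.6 itself lists ITI as a reason for administration distinct from prophylaxis and from treatment of a bleed. The argument that takes PK doses out of consumption therefore applies equally to tolerance-induction doses, yet they stay in.

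ITI can last up to 24 months (SAP 3.1.2.3), so ITI time can make up most of a child's denominator and ITI doses most of his numerator. His overall value would then describe mainly his ITI regimen. With about 30 patients planned, a few such children could move an overall mean.

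**Working it through.** The documents state no consumption figure to reproduce. The check has two parts.

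**Is ITI inside the overall value?**

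- The efficacy period ends with the last regimen, and ITI can be that regimen (SAP 5.4.2, 5.3.2).
- SAP 6.6.2.2 assesses compliance with prophylactic and ITI dosing during the efficacy period, which places ITI inside it.
- SAP 6.6.1.5, the next section after consumption, expressly leaves out the ITI period for last prescribed dose. SAP 8 limits the incremental recovery summary to the episodic and prophylactic regimens. SAP 6.6.1.4 has no such restriction.
- ITI requires a confirmed positive inhibitor (Protocol 10.2.6.5), so all ITI time falls after the last negative test preceding that inhibitor. Protocol 16.2.1 would therefore remove all of it from the main efficacy summary.
- SAP Section 10 lists the major differences from the protocol and does not mention giving up that cut.

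**How much could it matter?**

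Document inputs: 50 IU/kg weekly starting prophylaxis (SAP 3.1.2.2), 24 months maximum ITI, about 30 patients (SAP 3.3). Assumptions for illustration only: the ITI dose rate, the time on prophylaxis before ITI, one ITI child, and the other 29 children at the reference value.

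Reference: 50/7 × 365.25 = 2,609 IU/kg/year.

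For a child with p years of prophylaxis, then i years of ITI at m times the prophylactic rate, the SAP formula gives r × 2,609, where r = (p + m·i)/(p + i). The mean of 30 is multiplied by (29 + r)/30. With p = 0.5 and i = 2:

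| m (assumed) | r | Child's overall value | Mean of 30 | Rise |
|---|---|---|---|---|
| 1 | 2.5/2.5 = 1.0 | 2,609 | 2,609 | 0% |
| 2 | 4.5/2.5 = 1.8 | 4,696 | 2,679 | 3% |
| 4 | 8.5/2.5 = 3.4 | 8,870 | 2,818 | 8% |
| 7 | 14.5/2.5 = 5.8 | 15,132 | 3,026 | 16% |

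With three such children, the rise is 3 × 0.8/30 = 8% at m = 2 and 3 × 4.8/30 = 48% at m = 7.

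Extreme assumed case: 20 weeks (140 days) of prophylaxis, then 24 months (730.5 days) at 200 IU/kg/day, which is 200/(50/7) = 28 times the prophylactic rate.

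- Child: (50/7 × 140 + 200 × 730.5)/(140 + 730.5) × 365.25 = 147,100/870.5 × 365.25 ≈ 61,700 IU/kg/year.
- Mean of 30: (29 × 2,609 + 61,700)/30 ≈ 4,579, a rise of about 76%.

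The SAP reports the median beside the mean (5.1.1.1). One outlying child among 30 shifts the median by at most about one rank.

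**The case against.** The strongest reply is that the SAP may never display an overall mean. SAP 6.6.1.4 only derives the overall value and refers to 7.4.7 for its summary. SAP 7.4.7 presents the table by treatment regimen, SAP 5.1.1 says efficacy presentations generally have no overall column, and the table list names consumption by regimen only. This stands as a limit on reach. A reader might infer that the prophylactic or episodic results are inflated, or that the SAP commits to reporting a distorted overall mean. The documents support neither: each regimen column holds only time on that regimen, and ITI has its own column. The overall value is nevertheless required by 6.6.1.4, would reach the listing of dose and consumption endpoints, and is what Protocol 16.2.3 asks to have summarized.

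Second, the authors may have meant to leave ITI out. The evaluability rule in 5.4.2 names only episodic and prophylactic regimens, and 5.4.4 defines a separate ITI period. That is plausible, but no sentence takes the ITI period out of the efficacy period, and 6.6.2.2 points the other way.

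Third, rFIXFc may be given for active bleeding during ITI (Protocol 10.2.6.6). Those doses do fit the endpoint wording, so the parallel with PK doses holds for tolerance-induction doses and not for every dose in the ITI period. This stands. It is met by reporting post-inhibitor consumption separately, as the protocol provides.

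Fourth, a cut at the start of ITI would stop short of the protocol's cut. It would keep post-inhibitor doses given before ITI, including those of low-titer patients continuing at the same or a higher dose (Protocol 10.2.6.2). This also stands and determines the fix.

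**Conclusion.** The point holds in a confined form. As written, the overall per-patient consumption in SAP 6.6.1.4 mixes ITI with prevention and treatment of bleeding. This conflicts with the endpoint definition, with the SAP's own reason for removing PK doses, and with Protocol 16.2.1, and Section 10 does not declare it. The primary endpoint and the regimen-specific consumption results are untouched.

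The size cannot be fixed from the documents, because the ITI regimen is the Investigator's choice and the number of ITI patients is unknown. For one ITI child among 30 the mean rises by 0% to 16% at assumed rates of 1 to 7 times prophylaxis. The 76% figure needs 28 times that rate for the full 24 months and should be read as an extreme, not as an expectation. If no patient enters ITI, nothing changes.

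**What to change.** - In SAP 6.6.1.4, for the overall consumption value only, end each inhibitor patient's data at the last negative inhibitor test, as Protocol 16.2.1 requires. Specify this as the last negative test before the confirmed inhibitor, since successful ITI produces later negative tests. All ITI doses and days then leave both numerator and denominator.
- Report post-inhibitor and ITI consumption separately, including rFIXFc given for bleeds during ITI.
- If the sponsor prefers a different cut, at minimum exclude the ITI period from the overall value and list the departure in Section 10.
- State in 7.4.7 whether the overall value is tabulated.

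The cost is a few sentences in the SAP and one date filter in programming. Regimen dates, injection reasons and inhibitor test dates are already collected, so no new data are needed.
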